Assessment of volume status will use the following surrogate markers of volume overload: IDWG >2.5kg, relative IDWG >5.7% of the TW, and UFR >10ml/kg/hr. Events of volume overload will be compared between study groups as proportion of markers of volume overload of the total measurements of IDWG and UFR achieved with each HD treatment during the first 3 months, stratified in two periods (week 1 to 6 and week 7 to 12).

- Hospitalization rate

Time point: end of follow-up

Time to first hospitalization, cause of hospitalization and length of stay will be recorded and compared between treatment arms.

- Quality of life, Depression and Anxiety

Time points: weeks 6 & 12

The Dialysis Symptom Index questionnaire will be used to assess participant health-related quality of life. This is a short form that measures the burden of kidney disease, symptoms/problems of kidney disease, and effects of kidney disease scales. The score range is 0-100 with higher scores denoting better outcomes. Depression will be assessed using the PHQ-9 instrument. Anxiety will be assessed using the GAD-7 instrument.

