## **Methods and Measures**

### **Design**

This randomized pilot trial will be parallel-arm in design. We will enroll 50 patients of age  $\geq 18$  years, with incident ESKD. Participants will be equally randomized to one of the two regimens: a) twice-weekly HD plus adjunctive pharmacologic therapy (loop diuretic, potassium-binding agent, and sodium bicarbonate) for six consecutive weeks, continued by thrice-weekly HD (intervention group); or b) thrice-weekly HD (comparator group) (Appendix A). Patients will be followed for 12 months after the date of randomization; or until transplant, death, withdrawal of consent, or transfer of care outside Wake Forest healthcare system, whichever occurs sooner. Feedback from the participants will be obtained during the study to (1) evaluate the delivery of study-related information, (2) evaluate coordination of care during the study as it pertained to study-related procedures, (3) evaluate patient perceptions on study-related assessments, (4) elicit patients' motivations for study participation, and (5) obtain participant input regarding future research concerning the study intervention.

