### **Sample Size**

The primary purpose of this pilot study is to evaluate the feasibility of a randomized intervention between a stepped regimen of HD and a standard regimen of HD. Therefore, for the primary feasibility outcome, we elect a pilot trial sample size of 50 patients total (25 patients per treatment group) which is consistent with recommendations for pilot and feasibility studies where samples of 10 to 20 participants per group have been deemed adequate to assess feasibility outcomes (Stat Methods Med Res 2016, 25(3), pp. 1057-1073). Power calculations for a future multicenter clinical trial will be carried out using the effect size on RKF and variability collected during this pilot study.

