Dialysis prescription (HD treatment time and frequency of administration, achieved blood flow, dialysate flow, potassium and calcium dialysate baths), vascular access used for HD, target weight (TW), inter-dialytic weight gain (IDWG), and ultrafiltration rate (UFR) will be recorded throughout the study. Relative IDWG will be expressed as percentage of TW when divided by the nephrologists' determined target weight. All hospitalizations and deaths (along with the cause) will be recorded from the time of enrollment to study end.

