For evaluation of primary safety end points and secondary clinical end points, intention-to-treat principles will be followed. Evaluation of categorical end points will be performed using chi-squared tests. Evaluation of continuous end points will be performed using Student's unpaired t-test for normally distributed variables, or the Wilcoxon rank-sum test for nonparametric data. For comparison of variables measured during the time course of the study, a repeated measures analysis of variance (ANOVA) will be used. The consistency of effects on the primary end point will be explored in a variety of subgroups. Kaplan–Meier methods will be used for time-to-first hospitalization analyses. Missing RKF data for subjects will be replaced (rather than excluding them from the analysis, as missing RKF measurements might not be completely at random) using linear regression to estimate values based on other measurements for each subject (linear trend at point, SPSS). For each group-sequential analysis, the upper bound of the one-sided confidence interval for the hazard ratio (incremental HD to conventional HD) would be calculated with the use of the critical value from the Lan–DeMets–O'Brien–Fleming alpha-spending function, which preserves an overall one-sided alpha of 0.025. No adjustments for multiplicity will be made. An independent Safety Monitoring Committee will review all available data on a quarterly basis. Analyses that signal safety concerns (i.e., higher rates of hospitalization, treatment failure or death in the intervention arm compared to the comparator arm) will be reported to an independent Steering Committee to determine whether the study should be discontinued, be modified and then proceed, or continue with caution.

Descriptive statistics will be used to report the results of Participant Feedback Questionnaire.

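### Length of stay is compared between arms with no stated unit and no value for patients never admitted; on its ordinary meaning, the comparison can favour an arm with extra short admissions

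*Combined protocol and SAP*

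**What the plan says.** The combined protocol and SAP lists "Hospitalization rate" among its secondary outcomes, assessed at the end of follow-up. The whole definition is: "Time to first hospitalization, cause of hospitalization and length of stay will be recorded and compared between treatment arms". Despite the heading, no count or rate of admissions is among the items to be compared.

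The Analytical Plan has three statements that bear on this:

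- Continuous end points are to be compared by Student's "unpaired t-test for normally distributed variables, or the Wilcoxon rank-sum test for nonparametric data". No other rule in the section fits length of stay.
- Kaplan–Meier "methods will be used for time-to-first hospitalization analyses".
- On the analysis set: "For evaluation of primary safety end points and secondary clinical end points, intention-to-treat principles will be followed".

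The Data collection section adds: "All hospitalizations and deaths (along with the cause) will be recorded from the time of enrollment to study end".

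No section gives the unit of length of stay, a value for patients who are never admitted, or a way to handle several stays by one patient.

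**The concern.** In ordinary use, a length of stay exists only once a patient has been admitted. Admission happens after randomisation and may itself be affected by the dialysis schedule. A comparison of stays, or of admitted patients only, therefore sets two selected groups against each other, and randomisation no longer makes them comparable. If single stays are the unit, an unpaired test would also treat repeat stays by one patient as independent.

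The direction of the possible error matters in this trial. The Human Subjects Protection section names fluid overload, uncontrolled hypertension, raised potassium and low bicarbonate as risks of twice-weekly dialysis. The Data and Safety Monitoring section singles out admissions for volume overload or hyperkalemia in the incremental arm for tracking. It also has intervention patients assessed at least weekly, against twice monthly in the comparator arm, and closer watching could bring earlier and shorter admissions in one arm only. If extra brief admissions occur there, average stay falls in that arm. A reader could take this as a benefit although its patients spent more time in hospital.

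**Working it through.** **Inputs.** From the documents: 25 patients per arm, 50 in total (2 × 25 = 50, which agrees with the Sample Size section); follow-up of 12 months or to an earlier transplant, death, withdrawal or transfer; the t-test or Wilcoxon rule. The documents give no admission rate, mean stay or standard deviation, so there is no figure of the plan's to reproduce. All admission figures below are assumptions.

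**Step 1: general condition.** Let an arm have n admissions of mean length L, and add e admissions of mean length s. The new mean stay is (nL + es)/(n + e). This is below L exactly when s < L, equals L when s = L, and exceeds L when s > L. Total days always rise, by es.

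**Step 2: illustration.** Comparator: 15 admissions of 5 days. Intervention: the same 15 plus 10 of 1 day.

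| | Comparator | Intervention | Ratio |
|---|---|---|---|
| Total days | 15 × 5 = 75 | 75 + 10 × 1 = 85 | 85/75 = 1.13 |
| Mean stay per admission | 75/15 = 5.0 | 85/(15 + 10) = 3.4 | 3.4/5.0 = 0.68 |
| Days per randomised patient | 75/25 = 3.0 | 85/25 = 3.4 | 1.13 |

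Stay per admission is 32% shorter while hospital days are 13% higher.

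**Step 3: other assumed inputs.** Start from 10 admissions of 6 days (mean 6.00; 60/25 = 2.40 days per randomised patient) and add extra stays in one arm.

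| Extra stays | Mean stay | Days per randomised patient |
|---|---|---|
| 3 of 2 days | 66/13 = 5.08 | 66/25 = 2.64 |
| 5 of 2 days | 70/15 = 4.67 | 70/25 = 2.80 |
| 8 of 2 days | 76/18 = 4.22 | 76/25 = 3.04 |
| 5 of 6 days | 90/15 = 6.00 | 90/25 = 3.60 |
| 5 of 9 days | 105/15 = 7.00 | 105/25 = 4.20 |

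Mean stay can fall, hold or rise. Days per randomised patient rise in every row.

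**Step 4: how often it would show with 25 per arm.** Simulation of 3,000 trials per setting, with at most one stay per patient; base admission risk 20%, 40% or 60%; mean stay 6 days; 20 percentage points more patients admitted in the intervention arm; Wilcoxon test at two-sided 0.05. Ranges are across the three base risks. Significance is counted only when the intervention arm also has the lower mean.

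| Intervention arm | Extra stays about 2 days | Extra stays about 6 days |
|---|---|---|
| Admitted only: shorter mean stay | 71–78% | 46–49% |
| Admitted only: significantly shorter | 11–12% | 1.3–1.4% |
| All randomised, zeros included: lower mean days | 30–37% | 11–17% |
| All randomised: significantly lower | under 1% | 0.1% or less |

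With short extra stays, the admitted-only comparison tends to favour the arm with more admissions. Counting zeros removes that tendency; the remaining 30–37% is chance in small arms.

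**The case against.** The strongest reply is that the plan never says length of stay is analysed per admission or among admitted patients only. The intention-to-treat sentence is compatible with total days per randomised patient, zeros included, and on that reading the problem disappears. This stands. A reader might infer that the plan breaks its own intention-to-treat rule, or that it treats repeat stays as independent. The documents do not support either as a statement of fact, because each depends on a unit they leave open. What remains is that the total-days reading is nowhere stated and is not the usual meaning of length of stay, so the unit could be chosen after the data are seen.

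A reader might also infer that an arm with more admissions will look better. That is too strong. It needs extra stays shorter than the existing average and, with 25 per arm, it is a tendency. If the unit were total days per admitted patient, extra stays in patients already admitted would raise the figure.

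Finally, extra admissions would not go unseen:

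- Time to first admission covers all patients, and causes of admission are compared.
- Admissions for volume, potassium and the other listed causes count in the primary safety outcome for the first 3 months.
- A higher hospitalization rate in the intervention arm is a named signal at the quarterly review, and a Safety Officer reviews every admission quarterly.

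This limits the harm but does not replace the missing analysis. The first uses only the first admission, the safety outcome ends at month 3 and is restricted by cause, and the reviews are monitoring. None compares total hospital days or repeat admissions to the end of follow-up.

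**Conclusion.** The concern holds in a limited form. The unit of length of stay and the handling of patients never admitted are undefined. On the ordinary meaning, the comparison is not protected by randomisation, and it can favour an arm with additional shorter-than-average admissions while that arm's patients spend more days in hospital.

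The illustrated size (32% shorter stay, 13% more days) rests wholly on assumed admissions. The direction depends on the extra stays being shorter than average. The documents do not show that such admissions will occur.

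The consequence is modest. This is one of three items under a secondary outcome in a 50-patient pilot, none of the four feasibility criteria uses it, and the twice-weekly schedule is planned for six weeks of a 12-month follow-up. The change is still worth making, because a measure that keeps every randomised patient can be built from data already planned.

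**What to change.** In the Secondary outcomes and Analytical Plan sections, at the existing end-of-follow-up time point:

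1. Define the compared measure as total days in hospital per randomised patient, with zero for anyone never admitted, relative to that patient's follow-up time. This accommodates early exit through transplant, death, withdrawal or transfer.
2. Name one method in advance, for example a rank test on days in hospital per unit of follow-up, or a negative binomial model with a follow-up offset.
3. Report the admission rate by arm beside it, so that the outcome matches its heading.
4. Report length of stay per admission descriptively only.

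The cost is wording and a little extra analysis. All hospitalizations and length of stay are already to be recorded, so total days can be obtained by summing stays. The documents do not mention admission and discharge dates, so the sponsor should confirm that length of stay is captured for every admission. The one loss is that length of stay per admission is no longer formally tested.

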### ***Exploratory outcome***

- Patient survival

Timeframe: end of follow-up

The tertiary outcome will consist of exploratory analyses to compare the mortality rate between the two schedules of HD.

### **Analytical Plan**

Feasibility will be assessed using descriptive data regarding eligible patients, enrolled patients, intervention compliance and adherence to study-specific assessments, and drop-out/withdrawal rate among each intervention. The proportion of people meeting each of the feasibility and protocol adherence endpoints with accompanying 95% confidence intervals (CI) will be estimated using skew-corrected score tests with a continuity correction. Progress from pilot to large scale trial will be considered as: i) continue the study without modifications (feasible as is) if all feasibility criteria are met; ii) continue with protocol modifications (feasible with

modifications); or iii) stop the main study (not feasible) if none of the four feasibility criteria was met.

For evaluation of primary safety end points and secondary clinical end points, intention-to-treat principles will be followed. Evaluation of categorical end points will be performed using chi-squared tests. Evaluation of continuous end points will be performed using Student's unpaired t-test for normally distributed variables, or the Wilcoxon rank-sum test for nonparametric data. For comparison of variables measured during the time course of the study, a repeated measures analysis of variance (ANOVA) will be used. The consistency of effects on the primary end point will be explored in a variety of subgroups. Kaplan–Meier methods will be used for time-to-first hospitalization analyses. Missing RKF data for subjects will be replaced (rather than excluding them from the analysis, as missing RKF measurements might not be completely at random) using linear regression to estimate values based on other measurements for each subject (linear trend at point, SPSS). For each group-sequential analysis, the upper bound of the one-sided confidence interval for the hazard ratio (incremental HD to conventional HD) would be calculated with the use of the critical value from the Lan–DeMets–O'Brien–Fleming alpha-spending function, which preserves an overall one-sided alpha of 0.025. No adjustments for multiplicity will be made. An independent Safety Monitoring Committee will review all available data on a quarterly basis. Analyses that signal safety concerns (i.e., higher rates of hospitalization, treatment failure or death in the intervention arm compared to the comparator arm) will be reported to an independent Steering Committee to determine whether the study should be discontinued, be modified and then proceed, or continue with caution.

Descriptive statistics will be used to report the results of Participant Feedback Questionnaire.

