### ***Primary safety outcomes***

Time point: end of month 3

The intervention of stepwise HD schedule will be considered safe, relative to standard HD schedule, if there will be no significant difference in severe adverse events between the two HD treatment groups during the first 3 months of the study.

Severe adverse event(s) will be defined as the requirement of one or more additional HD treatment(s) or hospitalization(s) for: (1) a condition related to poor volume control (i.e., clinically-determined volume overload, decompensated heart failure, or hypertensive urgency/emergency); (2) severe electrolyte imbalance (i.e., serum potassium  $>6.5\text{mEq/L}$ ); (3) severe metabolic acidosis (i.e., serum bicarbonate  $<15\text{mEq/L}$ ); (4) symptomatic uremia (i.e., uremic encephalopathy, uremic pericarditis); or (5) death associated with study intervention.

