### **Data and Safety Monitoring**

Participants in the intervention arm will have more frequent analysis of their clinical status and lab results. These evaluations will be done at a minimum frequency of once per week in the intervention arms, versus twice per month in the comparator arm according to standard of care. The study team members (principal investigator and co-investigators) will be responsible for the frequent analysis of the participants enrolled in the intervention arm. Participants enrolled in the comparator arm will be evaluated according to the standard of care by their nephrologist. The principal investigator will be responsible for the overall monitoring of the data and safety of study participants. The principal investigator will be assisted by other members of the study staff.

Events related to the type of HD regimen--such as admission for volume overload or hyperkalemia in the incremental HD arm--will be closely tracked. Events will be recorded electronically and reported to the principal investigator monthly. An independent Safety Officer, unblinded to treatment assignments, will review, on a quarterly basis, all events of hospitalizations and cause of hospitalization, within the study cohort. All concerns regarding the frequency of HD will be reported to the Wake Forest IRB. In addition, the principal investigator, Safety Officer, and members of the research group will carefully consider amendments (including halting the trial if necessary).

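### The plan sets a hospitalization rate as an outcome and safety signal but names only a time-to-first-admission analysis, with no follow-up-adjusted rate and no rule for admissions in progress at randomization

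*Combined protocol and SAP*

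**What the plan says.** The Objectives list hospitalization rate among the secondary aims. Under Secondary outcomes, the item headed as a hospitalization rate is then specified differently: "Time to first hospitalization, cause of hospitalization and length of stay will be recorded and compared between treatment arms". The Analytical Plan names one method specific to hospitalization, Kaplan-Meier, whose "methods will be used for time-to-first hospitalization analyses".

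The same section makes a safety concern out of "higher rates of hospitalization, treatment failure or death in the intervention arm compared to the comparator arm", without saying how such a rate is calculated. Under Data and Safety Monitoring, the Safety Officer reviews each quarter "all events of hospitalizations and cause of hospitalization, within the study cohort".

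On capture, Data collection states: "All hospitalizations and deaths (along with the cause) will be recorded from the time of enrollment to study end". The Design section, by contrast, runs follow-up for 12 months from the date of randomization, ending early at transplant, death, withdrawal of consent or transfer of care. The Setting, Interventions and Subject Recruitment sections all allow recruitment from the inpatient service.

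**The concern.** A rate and a time to first event are different quantities. In the named analysis, a patient admitted five times counts the same as one admitted once on the same day. The plan also lets patients leave early for four reasons. A raw count of admissions, or a chi-squared, t or Wilcoxon test on such counts, would therefore mix admission frequency with length of observation. No offset or per-patient-year measure is specified.

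The start of counting is a second gap. Consent precedes allocation, so enrollment and randomization need not coincide. A patient randomized while in hospital may or may not already have a first hospitalization, depending on how the text is read. If the index admission counts, that patient has an event at time zero and contributes nothing more to the Kaplan-Meier curve. Randomization balances such events on average, but they say nothing about treatment, and 25 per arm leaves room for chance imbalance.

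At stake is whether the trial reports the quantity its objective names, and whether the committee reviewing higher hospitalization rates has a defined rate to look at.

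**Working it through.** **1. Text side by side.**

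| Place | Quantity |
|---|---|
| Objectives; outcome heading; safety signal | Rate of hospitalization |
| Outcome text | Time to first admission, cause, length of stay |
| Analytical Plan | Kaplan-Meier for first admission |
| Data collection | All admissions, from enrollment |
| Design | Follow-up from randomization, unequal between patients |

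No passage gives admissions per patient-year, a recurrent-event model or an index-admission rule. The group-sequential hazard ratio in the Analytical Plan names no event. The documents state no admission rate and no power for this outcome, so there is no figure of theirs to reproduce.

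**2. Share of admissions outside a first-event analysis.** Let m be mean admissions per patient over 12 full months and k the between-patient (gamma) variance. Then share = 1 − P(at least one)/m, with P = 1 − exp(−m) for k = 0 and P = 1 − (1 + km)^(−1/k) otherwise.

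Example with m = 1, k = 0.5: P = 1 − 1.5^(−2) = 0.556, so the share is 44%.

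The share passes one half only when m exceeds 1.59 (k = 0), 1.24 (k = 0.5), 1.00 (k = 1) or 0.84 (k = 1.5).

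With drop-out of 0.25 per year, k = 0.3 to 0.8 and no arm difference, the shares are:
- 0.5 admissions per year: about 25% to 30%
- 1.0 per year: about 40% to 47%
- 1.7 per year: about 55% to 60%

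**3. Power if the effect lasts all year.** The inputs are 25 per arm (Sample Size section), one year, drop-out 0.25 per year, true rate ratio 2 and two-sided 0.05. All but the sample size and the year are assumptions. There were 1,500 simulated trials per scenario, with about 1 point of Monte Carlo error.

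| Control rate | k | First-event log-rank | All-admissions rate model | Gain (points) |
|---|---|---|---|---|
| 1.0 | 0.3 | 40% | 60% | 20 |
| 1.0 | 0.8 | 28% | 45% | 17 |
| 1.7 | 0.3 | 42% | 74% | 32 |
| 1.7 | 0.8 | 25% | 53% | 28 |

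A separate simulation (20% loss, robust-variance rate ratio) gave 28% v 38% at 0.5 per year with k = 0.5, a gain of 10 points. At 1.7 per year with k = 0 it gave 58% v 94%, a gain of 36 points. Type I error was about 4% to 6% for both tests.

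**4. Power if the effect is confined to weeks 1 to 6.** The assigned regimens differ for 6 of 52 weeks. An early ratio of 4 averages to (4 × 6 + 46)/52 = 1.35 over the year, and an early ratio of 2 averages to (2 × 6 + 46)/52 = 1.12.

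| Control rate | k | Early ratio | First-event | Rate model |
|---|---|---|---|---|
| 1.0 | 0.3 | 4 | 21% | 19% |
| 1.0 | 0.8 | 4 | 17% | 16% |
| 1.7 | 0.3 | 4 | 34% | 23% |
| 1.7 | 0.8 | 4 | 23% | 17% |
| 1.0 and 1.7 | 0.3, 0.8 | 2 | 7–9% | 6–9% |

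Here the 12-month rate gains nothing and can do worse, because early excess is diluted by later admissions under the same assigned schedule.

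**The case against.** The strongest reply is that repeat admissions are not ignored. Cause and length of stay are also compared. Admissions for listed causes enter the primary safety outcome at month 3, which is defined by "the requirement of one or more additional HD treatment(s) or hospitalization(s) for" those causes. The safety reviewers see every admission. This stands as far as it goes: admissions are monitored and recorded, and none is lost. It does not supply a rate. The month-3 outcome is cause-specific and short, and the reviewers are told to look for higher rates without a definition of one.

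A reader might infer that the first-event analysis throws away more than half of admissions and is a much weaker test for harm. The documents do not support this. They give no admission rate, and the share passes one half only above roughly 0.8 to 1.6 per patient-year. The power advantage needs an effect that persists well beyond the six weeks in which the schedules differ. Persistence is possible, for instance through preserved kidney function, which the plan hypothesizes, but it is not established.

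A reader might also infer that there is no time zero at all. The Design section gives one, the date of randomization. The gap is the conflict with enrollment in Data collection and the missing index-admission rule.

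Finally, this is a secondary outcome in a pilot: "we elect a pilot trial sample size of 50 patients total (25 patients per treatment group"), chosen for feasibility and without a power calculation. That stands, and it limits the severity.

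**Conclusion.** The mismatch between outcome and analysis holds at any admission rate, because it rests on the text alone. A rate is named as an objective, an outcome and a safety signal, no follow-up-adjusted rate is specified, and the data to compute one will exist. The conflicting start points and the missing rule for an admission in progress also hold.

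The numerical cost is conditional. With drop-out of 0.25 per year and gamma variance 0.3 to 0.8, about 25% to 60% of admissions fall outside the named analysis at 0.5 to 1.7 per year with no arm difference. The power gain from counting all admissions is about 10 to 35 points if a rate ratio of 2 lasts the year, and nil or negative if harm is confined to the first six weeks. Neither method is reliably sensitive with 25 per arm when patients vary, so estimation with an interval is the realistic aim. The rate analysis should therefore stand beside Kaplan-Meier and not replace it. Severity is minor.

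**What to change.** In the Analytical Plan:

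- Keep time to first admission. Alongside it, report admissions per patient-year by arm, with a rate ratio and 95% CI from a negative binomial or robust-variance Poisson model. Use log follow-up time as the offset, with arm and vascular-access stratum as terms.
- Report this for the full 12 months and for a prespecified early window (weeks 1 to 6 or the first 3 months), so that early harm is not diluted.
- Use the same rate definition for the safety signal.
- Start the clock at randomization and align Data collection with the Design section. Do not count an admission in progress at randomization. For those patients, start time at risk at discharge, and report their number by arm.

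The cost is wording only, with no new data. There are two small downsides. A few frequently admitted patients carry weight in a rate, which the overdispersion term or robust variance reflects in the interval. Discharge also falls after randomization, so the delayed start is not strictly protected by it; reporting the numbers by arm shows whether this matters. The estimated rate and between-patient variance would also help plan the multicenter trial that the Sample Size section foresees.
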